Evaluating the Efficacy of Lateral Heel Wedges for Osteoarthritis of the Knee

NCT: 02254473 March 1, 2014

Evaluating the Efficacy of Lateral Heel Wedges for Osteoarthritis of the Knee

Principal Investigator: [name]

Significance

Given the prevalence of osteoarthritis of the knee and the general aging trends of the population it is important to develop effective non-operative interventions to reduce pain and improve function in the adult population with osteoarthritis (OA) of the knee. A large body of experimental evidence documents the potential for cartilage regeneration in the osteoarthritic joint under conditions of mechanical unloading of the involved joint. An easily applied, off-the-shelf shoe insert material that, when configured properly, will unload the medial compartment of the knee has been developed. The purpose of this investigation is to document the acceptability and effectiveness (with patient reported measures) of this insert compared to a control insert which does not unload the medial compartment of the knee in a group of patients with significant OA of the medial compartment of the knee in order to develop pilot data to document the effect size, acceptability of the inserts, compliance, feasibility, and power for a future clinical trial. Following communication with NIAMS officials we plan to submit an R34 proposal for this purpose. Multiple clinical trials measuring the impact of shoe inserts on knee OA symptoms report minimal benefit. These trials are conducted in a manner which used: 1. self-reported OA, 2. subjects not presenting for treatment and 3. Not in a stratified population of patients with moderate to severe medial compartment OA. Our study selects for patients with this moderate to severe medial compartment OA who pass the screening test of sufficient MCL laxity to allow correction of the weight bearing axis. Further the material used in these inserts is of a different stiffness which is molded to that of the human heel pad. This clinical trial will likely never be industry funded because of the inexpensive nature of the intervention.

Objectives and Hypothesis

Regularly wearing a 5 degree sloped insole over the course of one year will result in a wider joint space by x-ray in 60% of the subjects, a significant decrease in knee pain, decreased use of over the counter analgesics, and a clinically important 2 point improvement in the Womac pain and stiffness scale.

Methods

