This group would otherwise be candidates for surgical intervention. Those with end stage osteoarthritic lesion would have biological potential for restoration of the cartilage. They would have range of motion that provided near normal gait and flexion enough to rise out of a chair. The insole fitting would accommodate the candidate's foot anatomy, any pathology and the geometry of their shoe.

Rationale for exclusion:

This criterion removes those conditions that would have potential to add conflicting data to the study and/or produce discomfort for the subject.

Statistical analysis plan:

All analyses will be done using S.A.S. (version 9.2) and two-sided p-values of less than 0.05 will be considered statistically significant. Appropriate descriptive summary statistics (including means and s.d.) and graphs (including histograms, kernel smoothed density plots, error bar plots) will be utilized to summarize Womac pain, stiffness and function in each treatment group at baseline, 6 month visit and 12 month visit. We will consider a linear regression using the generalized estimating equation (gee) approach to estimate the Womac pain, stiffness and function differences between wedge insert and flat insert groups with intention-to-treat principle. We selected gee as the primary approach as it accounts for the potential correlations among repeated measures within subjects. In addition, it has been shown the gee is more efficient compared to the two sample t-test, the paired t-test, the analysis of covariance (including treatment and baseline response as covariates), and is asymptotically equivalent to the analysis of covariance ii (including treatment, baseline response and an interaction between treatment and baseline response as covariates) 40. Missing data will be handled with multiple imputation using S.A.S. proc mi and mianalyze. Secondary outcomes will include clinical and functional outcomes with standardized knee radiographs, a validated University of Minnesota pain and acceptability scale, a medication log in terms of weekly hours of insert usage will be analyzed similarly and the Tegner Activity Scale to document any change in activity level in addition to the function addressed in the other outcomes instruments

Test Intervention:

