The Insoles: A commercially available proprietary insole in the form of a slab 10.5 cm wide and 35.5 cm. long will be used. They are available in two geometries and materials. The control insole is blue in color with a thin felt cover to be next to the subject's skin. It is 3 mm level depth side to side and front to back. The material is a proprietary material known commercially as Poron® with a durometer of 25; the average durometer of the human foot is 25-35 depending upon the thickness of the plantar soft tissue and the presence of bone beneath.

The experimental insole is a slab is green in color and made of polyvinyl acetate with a felt layer opposite the patients skin. It has a 5 degree wedge and is 3 mm high on thin side and 10 mm high on the other side. This insole will be fitted with the pattern cut so the outer side of the foot would have the maximum depth of material (the highest side).

Study Procedures:

Patient related: We will recruit 80 subjects presenting for treatment of knee who have primary OA of the knee primarily involving the medial compartment and meet the inclusion criteria. The will be randomized via a random table generated computer program to the wedge inserts or the flat inserts. They will be screened for adequate knee laxity and subtalar motion before enrollment at each site.

Subjects, experimental and control, will complete the Womac based on their current function, have bilateral standing knee radiographs obtained in a standardized fashion and be fit with the inserts and instructed to return in 6 weeks to have new inserts fashioned. The patient contact will be performed by the clinical coordinator. At the 6-week visit, the patients randomized to the wedge insole will have the 5 degrees insoles fit after their 6-week adjustment period with the 2.5 degrees insoles while those in the control group will be fit with new inserts.

At 3, 6, 9 and 12 months, all patients will return for new inserts and to complete secondary radiographs (6 months only) and to turn in their shoe insert acceptability, use logs and medication logs. Patients will be supplied with as many inserts as they need to assure that the shoes they wear on a daily basis are included.

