At 1 year, a convenience sample of 5 patients in the wedge (treatment) group and 5 patients in the control group who have had prior knee MRI's within 1 year of institution of the treatment shoe inserts will have knee MRI's repeated to check the quality of medial compartment articular cartilage.

Statistical Analysis

The data analysis will be done in a blinded fashion by our statistician. The Womac and Tegner data will be analyzed with standard statistical approaches and confounding variables of medication use and time of use of the shoe inserts will be analyzed with regression techniques. Knee medial compartment width will be measured by two blinded radiologists.

Subject Instructions: Subjects will be informed they are eligible to be part of a study testing various insoles of differing color, material and shape for their impact on arthritic knee pain and function. They will be instructed on insertion and removal of the insoles including printed material of such instructions. After a 6 week run in period utilizing the 2.5 degree lateral wedge test article in order to adjust to the altered weight bearing axis, the subjects will have a 5 degree wedge test article fashioned in the same manner. They will be instructed to return at 3 month intervals for fitting of new insoles and clinical evaluation. X-rays , medication logs, U of MN pain scale¹, Tegner and Womac will be collected at enrollment, 6 weeks, 3 months, 6 months, 9 months and one year.

Tailoring the Insole:

An exam will be performed ensuring the subjects foot and ankle range of motion.

The existing insoles will be removed from both shoes. This method provides maximum toe box height. It also makes a more uniform insole material bilaterally thereby providing consistency. In both groups the insole will be tailored to the subject's anatomy, pathology, and existing shoe geometry. The subjects will be fitted with the tailored insole that extends from the back of the heel to just beyond the metatarsal head, thereby maximizing room in the toe box. Multiple tailoring may be necessary to achieve comfort. The subjects are instructed on the ease of removing and placing the insole so they can move them shoe to shoe, day to day. The insoles will be replaced every 3 months. The Study Coordinator at the local site will have printed instructions to facilitate and perform the fitting of the test and control inserts based on patient randomization.

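### Medication use and insert wear time are labelled confounders, but their on-study values arise after randomisation, and nothing keeps them out of a WOMAC or Tegner arm comparison

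*Combined protocol and SAP*

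**What the plan says.** The combined protocol and SAP describes the analysis in two places.

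- **Statistical analysis plan.** WOMAC pain, stiffness and function are to be compared by linear regression with GEE, estimating "differences between wedge insert and flat insert groups with intention-to-treat principle". On the choice of method it says: "We selected gee as the primary approach as it accounts for the potential correlations among repeated measures within subjects". Neither medication use nor wear time is named as a covariate. Among the secondary outcomes is "a medication log in terms of weekly hours of insert usage will be analyzed similarly". That sentence is garbled, but it places the medication log and weekly insert hours on the outcome side.
- **Statistical Analysis** (the short section after the MRI paragraph). WOMAC and Tegner are to be analysed by standard approaches. The same sentence adds that "confounding variables of medication use and time of use of the shoe inserts will be analyzed with regression techniques". It does not say which values are used (baseline or on-study), which model they enter, or whether that model is supportive.

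Three other places bear on the role of these variables.

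- **Objectives and Hypothesis** expects the wedge to lead to "decreased use of over the counter analgesics".
- **Study Procedures** has patients attend at 3, 6, 9 and 12 months and, among other things, "to turn in their shoe insert acceptability, use logs and medication logs". **Table 2** marks both logs as not done at the randomisation visit and as collected from 6 weeks on.
- **Subject Instructions** differs on the medication log: "X-rays , medication logs, U of MN pain scale¹, Tegner and Womac will be collected at enrollment", and then at each later visit.

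**The concern.** A confounder of a treatment comparison has to influence assignment or share a cause with it. Randomisation rules that out for anything that happens afterwards. Wear time cannot exist before an insert is fitted. On-study analgesic use follows assignment and is expected to respond to it. The plan therefore gives the same quantities three roles: hypothesised effect (medication), secondary outcomes (both) and confounders (both).

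An analyst who takes the third role literally would add both as regressors beside treatment arm. The arm coefficient would then compare patients with equal medication use and equal wear, which is not the comparison that randomisation protects.

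The stakes reach beyond this trial. Under Significance, the study is to supply "pilot data to document the effect size, acceptability of the inserts, compliance, feasibility, and power for a future clinical trial", and the paragraph on the R34 submission says that its data will be used to calculate the size of the definitive trial. No text says which estimate serves as the pilot effect size.

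**Working it through.** The plan states no power, SD, dropout or covariate effect, so it has no figure to reproduce. The first step is textual. The second illustrates size on assumed inputs.

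**Timing and role**

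- Wear time: necessarily post-randomisation, and Table 2 agrees.
- Medication use: every log value is post-randomisation on Table 2's schedule. On the Subject Instructions schedule there is also an enrollment value, which would be a legitimate covariate. On-study values are post-randomisation on either schedule.
- Covariates in the Statistical analysis plan: the only ones mentioned are treatment, baseline response and their interaction, where GEE is compared with forms of analysis of covariance. No list is given and nothing is excluded.

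**Assumed inputs**

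80 subjects (from the plan) split 40 and 40 (assumed); one timepoint; ordinary least squares; within-arm outcome SD of 1; negative values mean benefit; two-sided 0.05 (from the plan). For an adjusted model with residual SD s, and an arm difference of d within-arm SDs in the covariate, SE ≈ s × sqrt(2/40) × sqrt(1 + d²/4). Power and error rates are from 20,000 simulated trials per setting, except that the 5% for equal wear follows from theory.

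**(a) Medication M only tracks pain.** Y = -0.5T + U and M = Y + e, with within-arm correlation r between M and Y. The within-arm slope of Y on M is r², and the arms differ by -0.5 in M. So the adjusted coefficient is -0.5 - r²(-0.5) = -0.5(1 - r²), with residual SD sqrt(1 - r²).

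- Unadjusted: -0.50, SE 0.224, ratio 2.24, power 60%.
- r = 0.3: -0.5 × 0.91 = -0.455, residual SD 0.954, SE 0.214, ratio 2.13, power 55%.
- r = 0.5: -0.5 × 0.75 = -0.375, residual SD 0.866, SE 0.195, ratio 1.92, power 47%.

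A planner who took both coefficient and residual SD from the adjusted model would see a standardised effect of 0.455/0.954 = 0.477 or 0.375/0.866 = 0.433. For 80% power that means 70 or 85 per arm, against 64 at 0.50.

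**(a′) Analgesics also lower pain.** Let P = -0.5T + U, M = P + e and Y = P - bM, with r = 0.5 between M and P. The adjusted coefficient stays at -0.375. The unadjusted total effect is -0.5(1 - b): -0.45, -0.40 and -0.35 for b = 0.1, 0.2 and 0.3. Adjustment understates the effect in the first two cases and overstates it in the third.

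**(b) Wear time W, no true effect.** Y = U and W = -gT - hU + e, with unit within-arm SD, so the wear-pain correlation is -h. The adjusted coefficient is -gh.

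- g = 0 (equal wear): no bias, type I error about 5%.
- g = 0.25: -0.075 (h = 0.3) or -0.125 (h = 0.5); type I error about 6% or 10%.
- g = 0.5: -0.15 (h = 0.3) or -0.25 (h = 0.5); type I error about 10% or 23%. In the last case SE = 0.866 × 0.2236 × sqrt(1.0625) = 0.200 and the ratio is 1.25.

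**Repeated measures.** These figures do not carry over directly to a five-visit GEE. At r = 0.5 the coefficient remains -0.375 only if the noise in medication use has the same within-subject correlation as pain. With visit-independent noise it is about -0.40, -0.43 and -0.46 for pain correlations of 0.4, 0.6 and 0.8. With noise correlation 0.8 and pain correlation 0.4 it is about -0.29.

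**The case against.** The best defence is that the sentence describes two analyses: its clauses have different subjects and different methods, and it never says that WOMAC or Tegner will be adjusted. The Statistical analysis plan makes an intention-to-treat GEE the primary approach, and the covariates that it mentions point to a baseline-only model. Compliance is a stated pilot aim, so relating wear time to outcome is a reasonable exploratory question.

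Much of this stands. A reader might infer that the primary WOMAC analysis is biased, or that the next trial will be sized on an adjusted coefficient. The documents support neither. The primary model names neither variable, and the primary GEE is the natural source of the pilot effect size. Nor do the documents record any difference in wear between arms, and an enrollment medication value, if collected, would be a proper covariate.

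The defence does not close the gap. Intention-to-treat fixes who is analysed and in which arm, not the covariates. The GEE is something the authors will consider, and that sentence covers WOMAC only; Tegner appears at the end of the garbled secondary-outcome sentence. The confounder label itself invites adjustment, and no text marks the regression as supportive.

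**Conclusion.** The point holds as a risk that the wording leaves open, not as a demonstrated error in the primary result. The label is wrong for on-study values and conflicts with the role that the plan gives these variables elsewhere. Any WOMAC or Tegner arm estimate taken from the regression in the Statistical Analysis section would not be the intention-to-treat effect.

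The size cannot be fixed from the documents. The single-timepoint illustration shows that it could matter: up to a quarter of a -0.50 SD effect removed at r = 0.5, or type I error of about 23% at the most adverse wear setting tried. It also shows that there is no bias from wear time when wear is equal, and no fixed direction once analgesics themselves relieve pain. It would be too strong to say that adjustment always dilutes the effect.

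This should be fixed. Confidence is medium, because the sentence can be read as a separate analysis.

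**What to change.** In the Statistical Analysis section:

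- Drop the word confounding.
- State that the WOMAC and Tegner arm comparisons use only arm, visit and pre-randomisation covariates (baseline score, and baseline medication use if it is collected).
- Analyse medication use and wear time as outcomes by arm, as the Statistical analysis plan already intends.
- Label any model that adjusts for their on-study values as exploratory.
- State that the pilot effect size comes from the intention-to-treat GEE.

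Separately, reconcile Subject Instructions with Table 2 on whether the medication log is collected at enrollment. That decides whether a baseline medication covariate exists.

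The cost is a few sentences and one schedule reconciliation. No new data are needed.

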We will recruit 80 adults with Kellgren-Lawrence changes between grade 2-4 medial compartment osteoarthritis of the knee from the TRIA Orthopaedic Center in Minneapolis, MN. The subjects will be randomized to a 5 degrees lateral wedge shoe insert or a flat shoe insert of similar properties through a random table generator application which will be coordinated through the TRIA Orthopaedic Center.

Inclusion Criteria:

- Adult patients 30 years or older with symptomatic medial compartment knee osteoarthritis and Grade 2-4 Kellgren-Lawrence radiographic changes presenting for treatment of knee pain.
- Range of motion knee-flexion beyond 100 degrees and not lacking more than 15 degrees of extension.
- Subtalar and forefoot motion permitting foot/ankle eversion with weight bearing.
- Sufficient shoe toe box height to allow space for the insole and therefore comfort and compliance.
- Passive laxity of medial capsule and collateral ligament by knee extension test.

Exclusion Criteria:

- All other forms of knee arthritis other than osteoarthritis.
- Bilateral symptomatic osteoarthritis of the knee.
- Knee Instability- medial pseudo-opening of greater than grade 1 or detectable anterior-posterior instability.
- Less than Grade 2 Kellgren-Lawrence radiographic changes in the medial compartment of the knee.
- Kellgren-Lawrence radiographic changes that are greater than or equal to the medial compartment in either the patellofemoral or lateral compartment.
- Inadequate knee range of motion as demonstrated on exam.
- Balance problems requiring the use of a walker or wheel chair (ambulation with aid).
- Diabetes with peripheral neuropathy.
- History of knee arthroscopy on the index knee within the past three months of study enrollment.
- History of reconstructive (ligamentous etc.) knee surgery within one year of enrollment.
- Intra-articular steroid injection or visco supplementation on the index knee within 1 month of study enrollment.
- Stiff subtalar or forefoot joints as demonstrated on clinical exam.
- Inadequate shoe toe box depth to accommodate the shoe insoles.
- Charcot joint.
- Fixed contracture of the medial capsule and/or collateral ligament as demonstrated on clinical exam.

Rationale for Inclusion:

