The subjects have end stage osteoarthritic lesions with potential for cartilage regeneration based upon the literature. Avoidance of surgery is advantageous to the patient. The material properties of the insoles are known. The durometer of the material is known which is relevant to the human plantar surface hardness. The material has an immediate memory to restore shape and depth which is a shorter interval than the human tissue on the plantar surface it is contacting. The fitting method provides the best opportunity for subject comfort and therefore compliance. The removal of the existing insoles removes a variable. The patient instruction during the fitting process; placement, removal and replacement educates them on the means of moving insoles from one shoe to the next. Insoles replacement every three months insures effectiveness of the material properties. The duration of the clinical trial is one year, a time sufficient to be compared to the time interval reported following high tibial osteotomy for cartilage to regenerate in similar lesion²²

Strengths of the proposed intervention:

The method of tailoring the insoles for anatomical and pathological customization should minimize discomfort and increase compliance. The plain film standing x-ray with measured joint space is a clear marker for change. The final MRI is a valid means of measuring cartilage volume and nature. The measurement emphasizes anatomical and pathological variables, thereby removing subjectivity. The single subjective outcome measure will be the Womac. The cost of the insert to the patient would be far less than if a custom insert was constructed into the shoe or any other form of treatment, surgery or otherwise.

C) Research Timeline

	6 months	12 months
Specific Aim 1	Regulatory Paperwork Approval, Study Orientation for staff, and patient enrollment	Patient Follow-up, data analysis, project completion

References

- 2. Bellamy N. Pain assessment in osteoarthritis: experience with the WOMAC osteoarthritis index. Seminars in Arthritis and Rheumatism. 1989;18(4, Supp. 2):14-17. PBS Record: 130

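### Medial compartment width is the only film measurement named, so lateral and other-knee narrowing is not systematically measured, and a coronal tilt present at filming could raise medial width without cartilage gain

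*Combined protocol and SAP*

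**What the plan says.** - **Measurement.** Statistical Analysis states: "Knee medial compartment width will be measured by two blinded radiologists". No section plans an outcome reading of lateral width, the other knee, joint-line angle or limb alignment. The lateral and patellofemoral compartments are graded for eligibility only (Exclusion Criteria).
- **Films.** Under Study Procedures, subjects "have bilateral standing knee radiographs obtained in a standardized fashion". Table 2 lists a bilateral standing AP view and a lateral view of the affected knee. The document does not define the standardization or say whether inserts are worn for the film.
- **Mechanism.** Significance describes patients "who pass the screening test of sufficient MCL laxity to allow correction of the weight bearing axis". The matching inclusion criterion is "Passive laxity of medial capsule and collateral ligament by knee extension test". Subject Instructions gives the reason for the 2.5 degree run-in: "in order to adjust to the altered weight bearing axis".
- **Both feet.** Tailoring the Insole says: "The existing insoles will be removed from both shoes". The stated aim is uniform material on both sides, so the other knee appears to be exposed. Whether a wedge is worn on that side is not spelled out.
- **Claim.** Objectives and Hypothesis expects that a year of wear "will result in a wider joint space by x-ray in 60% of the subjects", with no millimetre threshold, compartment or comparator rate. Strengths of the proposed intervention adds: "The plain film standing x-ray with measured joint space is a clear marker for change".
- **MRI.** At one year, a convenience sample of 5 patients per arm has repeat MRI to examine medial cartilage.

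**The concern.** The intervention works, if it works, by moving load away from the medial compartment. More load on the lateral side is the natural counterpart, and lateral narrowing is the structural harm that the mechanism suggests. The AP films show both compartments of both knees, but under the plan nobody records a follow-up width for three of those four compartments.

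The same mechanism affects how a positive result is read. In a knee chosen because its medial side can open, a larger medial gap may reflect cartilage gain, a tilt of the joint, or a mixture. Blinded reading does not help, because the readers would be measuring a gap that really is wider. The flat-insert control does not help either, because the axis shift is expected only in the wedge arm. The trial is meant to supply effect size and power for a definitive study, so a mechanical shift taken for structural benefit would carry into that design.

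**Working it through.** The document gives no effect size, SD or power for joint space, so there is no figure of the plan's own to reproduce. What follows shows how small a tilt would matter.

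**From the document:** medial width is the measured quantity; any widening counts; the target is 60% of subjects; 80 subjects in total; two-sided 0.05.

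**Assumed:** distance D between medial and lateral measurement points 40 to 50 mm; tilts of 0.5 and 1 degree; SD of measured change in medial width 0.3 to 0.8 mm; normal errors; 40 per arm; no cartilage change in either arm and no tilt in the control arm.

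**Step 1: medial opening from tilt.** Opening = r × tan(angle), where r is the distance from the pivot to the medial measurement point. With a midpoint pivot r = D/2 (20 to 25 mm). With a lateral pivot r = D (40 to 50 mm).

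| Pivot | r (mm) | 0.5 degree | 1 degree |
|---|---|---|---|
| Midpoint | 20 | 0.17 mm | 0.35 mm |
| Midpoint | 25 | 0.22 mm | 0.44 mm |
| Lateral | 40 | 0.35 mm | 0.70 mm |
| Lateral | 50 | 0.44 mm | 0.87 mm |

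**Step 2: shift that makes 60% of subjects wider.** The 60th percentile of the standard normal is 0.253, so the mean shift needed is 0.253 × SD: 0.08 mm at SD 0.3, 0.13 mm at SD 0.5 and 0.20 mm at SD 0.8. The tilt that produces it is arctan(shift / r). The smallest is arctan(0.076/50) = 0.09 degree and the largest is arctan(0.203/20) = 0.58 degree.

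**Step 3: effect of 1 degree of tilt in the wedge arm.** The share counted as wider is Φ(opening / SD).

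- Least affected case (r = 20 mm, SD 0.8): Φ(0.349/0.8) = 0.67. The chance that at least 24 of 40 are wider is 0.86. A between-arm comparison of means is significant with probability Φ(0.349 / (0.8 × √(2/40)) − 1.96) = 0.50.
- Most affected case (r = 50 mm, SD 0.3): all three figures exceed 0.99.
- With no tilt and no cartilage change, each subject has a chance of 0.5 of being wider, and P(at least 24 of 40) = 0.13.

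**Step 4: whether MRI can settle it.** With 5 per arm, the difference detectable with 80% power is (1.96 + 0.84) × √(2/5) = 1.77 SD (normal approximation). The sample is one of convenience and the stated target is medial cartilage. MRI is at 12 months, while Study Procedures and Table 2 place the only follow-up film at 6 months.

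**Step 5: whether lateral width alone is enough.** With a midpoint pivot, medial width rises and lateral width falls by the same amount, so their sum is unchanged. With a lateral pivot, medial width rises, lateral width stays put and the sum rises. True medial gain can give the same pattern of widths. The sum therefore cannot tell the two apart, and joint-line angle and the insert condition are needed as well.

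**The case against.** The strongest reply is that the tilt argument is conditional at every step. Tilt matters only if it is present when the film is taken. If the films are made without inserts, only lasting tilt or true lateral loss contributes. The document gives no figure for the tilt achieved. Medial pseudo-opening above grade 1 is an exclusion, which limits how lax the enrolled knees can be. All of this stands, and the millimetre figures above are an illustration, not an estimate of bias.

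On safety, bilateral symptomatic osteoarthritis is excluded, so the other knee is not a symptomatic osteoarthritic one. No rate of lateral harm is given. Radiographic measurement is also covered at the staff training meeting, so more may be read than one sentence states. These points lower the urgency, but none of them puts a lateral or other-knee reading into the plan.

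Finally, this is a pilot with WOMAC as the main analysis and radiographs listed as secondary. That is a fair argument about weight. Against it, joint space is named in the hypothesis, and the extra readings need no new film.

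A reader might infer that lateral harm is bound to go unseen. The document does not support that: the films show it and the lateral compartment is graded at screening. What is missing is a planned, systematic follow-up measurement.

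**Conclusion.** The gap is real and the remedy is a cheap improvement. Medial width is the only film outcome named. Lateral narrowing of the index knee, or narrowing in the other knee, would not be systematically measured, although the AP films already show it.

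If a tilt is present at filming, medial width could rise without cartilage gain. For 1 degree the addition is about 0.35 to 0.44 mm with a midpoint pivot and up to 0.70 to 0.87 mm with a lateral pivot. This rests on the assumed 40 to 50 mm spacing. The hypothesis counts any widening, and under the assumed SDs 0.09 to 0.58 degree would be enough for 60% of subjects to be wider.

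Two stronger readings are not supported. A reader might conclude that medial widening in this trial will be tilt counted as cartilage; the insert condition and the size of any tilt are unknown, so the document shows only that the two could not be reliably told apart. A reader might also take 0.70 to 0.87 mm per degree as the expected error in medial width. That is the change in the medial-minus-lateral difference, and for medial width alone it is an upper bound.

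**What to change.** Under Statistical Analysis:

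1. Have the same two blinded radiologists also measure lateral width and joint-line angle in the index knee, and medial and lateral width in the other knee, on every bilateral standing AP film already taken.
2. State that baseline and follow-up films are taken under the same insert condition, and say which one.
3. Report lateral narrowing of the index knee and narrowing of either compartment of the other knee by arm, as a safety outcome.
4. Interpret medial widening as structural benefit only alongside lateral width and joint-line angle. Do not use the medial-plus-lateral sum to separate tilt from cartilage gain.

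The film schedule must also be reconciled. Subject Instructions lists X-rays at every collection point from enrollment to one year, whereas Study Procedures and Table 2 give 6 months as the only follow-up film. The schedule decides what any lateral reading could show.

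The measurements need no new film, visit or reader: a short protocol addition and one table by arm. The price is slightly longer reading time and a stricter reading of medial widening.
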